8.4.1 Withdrawal from Study Drug

Patients permanently withdrawn from study drug should not be withdrawn from the study and, apart from study drug administration, should continue all scheduled study visits and procedures until the end of the scheduled treatment period at Day 56/Visit 8 (±3 days) to ensure complete follow-up (except in cases where the patient has withdrawn consent for study participation). The Follow-up Visit should take place 4 weeks after Day 56/Visit 8 (±3 days) regardless the date of definitive study drug discontinuation. If this is not possible, patients will be at least asked to return to the study site as soon as possible to complete the Early Termination and Follow-up Visit assessments as indicated in the Schedule of Assessments (Table 2).

If a patient discontinues study drug for any reason, the study site must immediately notify the medical monitor. The date and the reason for discontinuation must be recorded on the electronic case report form (eCRF).

In the event that a patient discontinues study drug prematurely because of a treatment-emergent adverse event (TEAE) or serious TEAE, the TEAE or serious TEAE will be followed up until it resolves (returns to normal or baseline values) or stabilises, or until it is judged by the investigator to no longer be clinically significant.

A patient may be withdrawn from the study drug at any time for reasons including, but not limited to, the following:

- Progressive disease: A rescue treatment may be initiated by the investigator according to clinical judgment as described in Section 9.6.2.
- Unacceptable toxicity or AE
- General or specific changes in the patient's condition that renders him/her ineligible for further treatment according to the inclusion/exclusion criteria (eg, suspected hypersensitivity to the study drug, pregnancy, etc)

Corneal healing is not a reason that study drug should be withdrawn before the end of the 8-week treatment period.

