12.7 Adverse Events

12.7.1 Adverse Events

An AE is any symptom, physical sign, syndrome, or disease that either emerges during the study or, if present at the Screening Visit, worsens during the study, regardless of the suspected cause of the event. All medical conditions (except those related to the indication under study) present at the Screening Visit will be documented in the medical history eCRF. Changes in these conditions and new symptoms, physical signs, syndromes, or diseases should be noted on the AE eCRF during the rest of the study. Clinically significant findings from laboratory assessments, vital signs measurements, ECGs, and other procedures that result in a diagnosis should also be recorded as AEs. Surgical procedures that were planned before the patient enrolled in the study are not considered AEs if the conditions were known before study inclusion; the medical condition should be reported in the patient's medical history.

Patients will be instructed to report AEs at each study visit. All AEs are to be followed up until resolution or a stable clinical endpoint is reached.

Each AE is to be documented on the eCRF with reference to date of onset, duration, frequency, severity, seriousness, relationship to study drug, action taken with study drug, treatment of event, and outcome. For ocular AEs, the eye (study eye or fellow eye) must be recorded on the eCRF as well. Furthermore, each AE is to be classified as being serious or nonserious. Changes in AEs and resolution dates are to be documented on the eCRF.

For the purposes of this study, the period of observation for collection of AEs extends from the time the patient gives informed consent until the last Follow-up Visit. Follow-up of the AE, even after the date of therapy discontinuation, is required if the AE persists until the event resolves or stabilises at a level acceptable to the investigator.

When changes in the intensity of an AE occur more frequently than once a day, the maximum intensity for the event should be noted. If the intensity category changes over a number of days, then those changes should be recorded separately (with distinct onset dates).

Specific guidelines for classifying AEs by intensity and relationship to study drug are given in Table 4 and Table 5.

Table 4. Classification of Adverse Events by Intensity

MILD: An AE that is easily tolerated by the patient, causing minimal discomfort and not interfering with everyday activities.

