- The number and percentage of patients reporting at least 1 related serious TEAE
- The number and percentage of patients reporting at least 1 TEAE leading to study drug discontinuation

- The number and percentage of patients reporting at least 1 ocular TEAE leading to study drug discontinuation
- The number and percentage of patients with AEs leading to death
- The number and percentage of patients reporting at least 1 AE of special interest
- The number and percentage of patients reporting at least 1 AE due to overdose
- The number and percentage of patients reporting at least 1 AE onset during the screening period
- The number and percentage of patients reporting at least 1 ocular AE onset during the screening period
- The number and percentage of patients reporting at least 1 AE onset during the treatment administration period
- The number and percentage of patients reporting at least 1 ocular AE onset during the treatment administration period
- The number and percentage of patients reporting at least 1 AE onset during the follow-up period
 The number and percentage of patients reporting at least 1 ocular AE onset during the follow-up period

Tabulations by SOC and PT will be produced for:

- All AEs (overall and by study period: screening, treatment administration and follow-up)
- Ocular AEs, overall and stratified for eye
- TEAEs
- Ocular TEAEs, overall and stratified for eye
- TEAEs by maximum intensity
- Ocular TEAEs by maximum intensity
- SAEs, overall, non-ocular and ocular, stratified for eye
- Serious TEAEs, overall, non-ocular and ocular, stratified for eye
- Related TEAEs (related to study drug and/or study procedure)
- · Related serious TEAEs
- TEAEs leading to study drug discontinuation, overall, non-ocular and ocular, stratified for eye
- AEs leading to death
- · AEs of special interest
- AEs due to overdose

These will be presented by SOC and PT, sorted by highest frequency within SOC and PT in the Total column. The 'All AEs' table will be presented by study period (overall, screening, treatment administration and follow-up). AEs that span multiple of these periods will only be counted once in the study period of the onset of the AE.

Patient listings will be generated for all AEs, all ocular AEs, all SAEs, TEAEs, AEs of special interest, AEs leading to study drug discontinuation, AEs due to overdose, and deaths.

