Related to Study Procedure	n (xx) m	n (xx) m	n (xx) m	n (xx) m	n (xx) m
Any Related Serious TEAE	n (xx) m	n (xx) m	n (xx) m	n (xx) m	n (xx) m
At least 1 TEAE leading to study drug discontinuation	n (xx) m	n (xx) m	n (xx) m	n (xx) m	n (xx) m

This document is confidential.

SAP Version: 1.0, 31-May-2024 Controlled Document ID: **3903A.02**, Effective Date 31-Aug-2020 Filing requirements: TMF

Sponsor: Recordati Rare Diseases; Protocol No.: REC0559-B-001

At least 1 ocular TEAE leading to study drug discontinuation	n (xx) m				
Study Eye	n (xx) m				
Fellow Eye	n (xx) m				
Both	n (xx) m				
Any AE leading to death	n (xx) m				
Any AE of special interest	n (xx) m				
Any AE due to overdose	n (xx) m				
Any AE onset during the screening period	n (xx) m				
Any ocular AE onset during the screening period	n (xx) m				
Study Eve	n (xx) m				
Fellow Eye	n (xx) m				
Both	n (xx) m				
Any AE onset during the treatment administration period	n (xx) m				
Any ocular AE onset during the treatment administration period	n (xx) m				
Study Eye	n (xx) m				
Fellow Eye	n (xx) m				
Both	n (xx) m				
Any AE onset during the follow-up period	n (xx) m				
Any ocular AE onset during the follow-up period	n (xx) m				
Study Eye	n (xx) m				
Fellow Eye	n (xx) m				
Both	n (xx) m				

n: Number of patients with data available, N: Number of patients within treatment group, m: Number of events

Note: Percentage is based on number of patients within treatment group.

Note: AEs of special interest (AESI) are defined as (1) corneal calcifications in the study eye, independent of intensity or (2) all non-serious AEs that are severe in intensity and considered related to the study drug as assessed by the investigator.

Note: If subjects experienced multiple AEs of different intensities, the subjects are counted only once in the respective catogory of the overall maximum intensity.

Note: The screening period is defined as the time from signed informed consent to treatment start date. The treatment administration period is defined from first treatment administration date to last treatment administration date. The follow-up period is defined as the 4 weeks following the last treatment administration date.

Analysis dataset: ADxx.SAS7BDAT; Data Source: Listing 16.2.x

This document is confidential.

SAP Version: 1.0. 31-May-2024

Controlled Document ID: 3903A.02, Effective Date 31-Aug-2020

Sponsor: Recordati Rare Diseases; Protocol No.: REC0559-B-001

Programming Note:

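### The SAP table shells end the AE follow-up period 28 days after last dose, but AEs are collected to the last Follow-up Visit, so AEs starting in between belong to no study period

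*SAP*

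**What the plan says.** **How the SAP defines the periods.** SAP 12.1 asks for all AEs to be tabulated overall and by study period (screening, treatment administration, follow-up), but its text does not define the periods. The definitions stand only in the shell footnotes of Tables 14.3.1.1 and 14.3.1.2. The treatment administration "period is defined from first treatment administration date to last treatment administration date". For follow-up: "The follow-up period is defined as the 4 weeks following the last treatment administration date". Table 14.3.1.1.1 takes over the footnotes of Table 14.3.1.1 for ocular events.

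**How an AE is assigned.** SAP 12.1: "AEs that span multiple of these periods will only be counted once in the study period of the onset of the AE". The programming note to Table 14.3.1.2 provides four displays: overall and the three periods. There is none for later onsets.

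**How long AEs are collected.** Protocol 12.7.1: "the period of observation for collection of AEs extends from the time the patient gives informed consent until the last Follow-up Visit". The last such visit is Visit 10, Day 84 ± 7 (Table 2 and section 10.11).

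**What happens after early discontinuation.** Under Protocol 8.4.1 patients withdrawn from study drug should keep attending through Day 56, and then: "The Follow-up Visit should take place 4 weeks after Day 56/Visit 8 (±3 days) regardless the date of definitive study drug discontinuation". The same section adds a fallback for those who cannot keep to this schedule: "patients will be at least asked to return to the study site as soon as possible to complete the Early Termination and Follow-up Visit assessments".

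**The concern.** Collection and reporting are anchored on different dates. For an early stopper, AE collection is tied to Day 56, while the reporting period is tied to the last dose. The two coincide only when Visit 10 falls within 28 days of the last dose.

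An AE starting on last dose + 29 days or later is in the database and in the overall counts, yet it is neither a treatment-period nor a follow-up AE. The affected outputs are:

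- the follow-up rows of Table 14.3.1.1, including study-eye and fellow-eye ocular AEs;
- the matching rows of Table 14.3.1.1.1;
- the follow-up page of Table 14.3.1.2.

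Protocol 7.2 gives collection of safety data after drug discontinuation as a purpose of the follow-up, so these rows will be read for that purpose. A reader who finds fewer events by period than overall has no footnote that explains the difference. If early stopping differs between arms, the shortfall can differ too.

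**Working it through.** **Inputs**

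- Reporting window after last dose: 28 days (shell footnotes, Tables 14.3.1.1 and 14.3.1.2).
- Last scheduled dose for completers: Visit 8, Day 56 ± 3, so Day 53 to 59 (Protocol 10.9).
- Last Follow-up Visit: Visit 10, Day 84 ± 7, so Day 77 to 91 (Protocol 10.11).
- Early stoppers who stay in the study: the same last visit, whatever the stop date (Protocol 8.4.1).

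**Formulas**

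End of reporting period = last dose day + 28.

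Uncovered days = max(0, Visit 10 day − end of reporting period).

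**The plan's own figure.** For a completer exactly on schedule, 56 + 28 = Day 84, the nominal Visit 10. The 4 weeks reproduces, with 0 uncovered days.

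**Completers off schedule**

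| Last dose | Period ends | Uncovered, Visit 10 at Day 84 | Uncovered, Visit 10 at Day 91 |
|---|---|---|---|
| Day 53 | Day 81 | 3 | 10 |
| Day 56 | Day 84 | 0 | 7 |
| Day 59 | Day 87 | 0 | 4 |

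**Early stoppers who attend to Visit 10**

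| Last dose | Period ends | Uncovered of post-drug days, Visit 10 at Day 84 | Uncovered, Visit 10 at Day 77 to 91 |
|---|---|---|---|
| Day 14 | Day 42 | 84 − 42 = 42 of 84 − 14 = 70 (60%) | 35 to 49 |
| Day 28 | Day 56 | 84 − 56 = 28 of 84 − 28 = 56 (50%) | 21 to 35 |
| Day 42 | Day 70 | 84 − 70 = 14 of 84 − 42 = 42 (33%) | 7 to 21 |

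**Who holds most of the uncovered time?** The documents do not say, so this part rests on assumptions: 108 patients, completers' last dose on Day 56, and Visit 10 uniform over Day 77 to 91. The mean completer gap is then (1 + 2 + … + 7)/15 = 28/15 = 1.87 days. Suppose 15% stop early (borrowing the dropout rate from the sample-size section), all at Day 14, and all attend to Visit 10:

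- early stoppers: 108 × 0.15 × 42 = 680 person-days;
- completers: 108 × 0.85 × 1.87 = 171 person-days;
- early stoppers' share: 680/(680 + 171) = 80%.

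Other assumptions move the share a long way:

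| Stop early | Attend to Visit 10 | Stop Day 14 | Stop Day 28 | Stop Day 42 |
|---|---|---|---|---|
| 15% | all | 80% | 73% | 57% |
| 15% | half | 67% | 57% | 40% |
| 5% | all | 54% | 44% | 28% |

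**Under the proposed definition.** With the period running to the end-of-study date, a patient followed to the last visit has 0 uncovered days, completer or early stopper.

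**The case against.** The 4-week window has a basis in the protocol. Section 7.1 plans 4 weeks of follow-up after the end of treatment, SAE and AESI reporting refers to 4 weeks after stopping drug (12.7.2 and 12.7.4), and elimination is expected to be rapid (7.2). A fixed window also gives every patient the same nominal follow-up length. Running to end of study puts up to 70 post-drug days for a Day 14 stopper beside about 28 for a completer, and includes time after rescue treatment.

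The comparability point stands and shapes the fix. It does not show that the window was meant as a risk period. The SAP gives no such rationale and does not list one among its changes from the protocol (2.3). TEAEs carry no upper time limit (12.1). The SAE and AESI reporting rules also cover the whole study, not only the 4 weeks after stopping.

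Three further points limit the concern, and all stand:

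- No AE is lost. Late AEs still count in the overall, TEAE, SAE and AESI outputs and in the listings, and the by-period displays are descriptive.
- Patient counts would not sum across periods under any definition, because one patient can have AEs in several periods. Only event counts could reconcile.
- Attendance to Day 84 after early discontinuation is requested but not certain: consent may be withdrawn, and 8.4.1 has a fallback.

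**Conclusion.** The point holds as a small, easily corrected reporting gap. Followed literally, the shells leave collected AEs with onset after last dose + 28 days in no study period. Follow-up AE counts can then be understated, and event counts by period can fall short of the overall count if such AEs occur. Screening and treatment-period counts are not affected.

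Per patient, the gap is weeks for an early stopper who attends to Visit 10 (42 days for a stop at Day 14, 28 for a stop at Day 28). For a completer it is 0 to 10 days, and the 10 requires the earliest Visit 8 with the latest Visit 10.

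A reader might infer two stronger statements that the documents do not support:

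- **That most of the missing AEs come from early stoppers.** Their share of uncovered time ranges from 28% to 80% in the scenarios tabulated, depending on how many stop, when, and whether they attend.
- **That the loss falls mainly on patients who stopped for worsening or intolerance.** Protocol 8.4.1 gives a list of reasons that is expressly not exhaustive, and nothing in the plan gives their frequencies.

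**What to change.** In the footnotes of Tables 14.3.1.1 (and so 14.3.1.1.1) and 14.3.1.2, define the follow-up period as running from the day after last administration to the end-of-study date. SAP 9.6 already uses that date to derive study duration. If a fixed 28-day window is also wanted, show two follow-up rows or pages: onset up to 4 weeks after last dose, and onset later than that. It would help to state the period definitions once in SAP 12.1, so that they do not stand only in the shells.

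The cost is one derivation and one repeated footnote. The downside is small: follow-up length will vary between patients and will include time after rescue treatment. The split rows or a footnote would make that visible.

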Patient ID/ Treatment group/ Region/ Disease stage \$/ Study eye	Informed Consent Date/ Date of PK Informed Consent *	Randomisation Date/ Randomisation Number	Treatment Start Date/Time	Treatment Termination Date (Study Day)/ Primary Reason/ Continued Schedule	Completed Study per Protocol?/ Protocol Version	Study Completion or Discontinuation Date (Study Day)/ Status
Xxxxx/ yyyy/ EU/ 2/ zzzzzz	ddmmmyyyy/ ddmmmyyyy	ddmmmyyyy/ xxxxx	ddmmmyyyy/ hh:mm	ddmmmyyyy (xx)/ Withdrawal by Subject/ No further visits	No/ 1.0	ddmmmyyyy (xx)/ Withdrawal by Subject
Xxxxx/ yyyy/ NA/ 3/ Zzzzz	ddmmmyyyy/ ddmmmyyyy	ddmmmyyyy/ xxxxx	ddmmmyyyy/ hh:mm	ddmmmyyyy (xx)/ Completed	Yes/ 2.0	ddmmmyyyy (xx)/ Completed
Xxxxx/ yyyy/ EU/ 2/ zzzzzz	ddmmmyyyy/ ddmmmyyyy	ddmmmyyyy/ xxxxx	ddmmmyyyy/ hh:mm	ddmmmyyyy (xx)/ Adverse Event/ Follow up visits only	No/ 1.1	ddmmmyyyy (xx)/ Adverse Event: xx
Xxxxx/ yyyy/ NA/ 3/ Zzzzz	ddmmmyyyy	ddmmmyyyy/ xxxxx	ddmmmyyyy/ hh:mm	ddmmmyyyy (xx)/ Other: xxxx	No/ 2.0	ddmmmyyyy (xxx)/ Other: xxxx

^{\$:} Stage 2 = Moderate, Stage 3 = Severe

Note: - = unknown or not evaluated, N/A = not applicable, NA = North America, EU = Europe

Note: Study Day 1 is the first day of study treatment.

Analysis dataset: ADxx.SAS7BDAT;
Date/time of run: ddmmmyyyy:hh:mm

program name>

Programming Note:

Display 'Adverse Event: xx' where xx is the AE number in case the patient discontinued due to an adverse event. If study discontinuation status is 'Other' specify reason xxxx as 'Other: xxxx'. If patient discontinued treatment add Continued Schedule information. Sort listing by treatment group (lowest REC 0/0559 to highest and then Vehicle) and patient ID. If a patient is not treated or a screen failure display 'Not Treated' or 'Screen Failure' in first column as Treatment group and sort these patients at the end of the listing.

This document is confidential.

SAP Version: 1.0. 31-May-2024

Controlled Document ID: 3903A.02, Effective Date 31-Aug-2020

^{*:} Only applicable for first 24 randomised patients

Sponsor: Recordati Rare Diseases; Protocol No.: REC0559-B-001

Listing 16.2.2.1 Protocol Deviations (Enrolled Set)

Patient ID/ Treatment group/ Region/ Disease stage \$/ Study eye	End of Treatment Status	Date of Deviation (Study Day)	Protocol Deviation	Protocol Deviation Term	Category
Xxxxx/ yyyy/ EU/ 2/ zzzzzz	Completed	ddmmmyyyy (xx)	Inclusion or Exclusion Criteria	Xxxxxxxxxxxx	Major
		ddmmmyyyy (xx)	Visit Window		Minor
Xxxxxx/ yyyy/ NA/ 3/ Zzzzz	Adverse Event	ddmmmyyyy (xx)	Study Procedure	Xxxxxxxxxxxx	Major
Xxxxxx/ yyyy/ EU/ 2/ zzzzzz	Other: xxx	ddmmmyyyy (xx)	Dosing	Xxxxxxxxxxxxx Xxxxxxxxxxxxxx	Major
Xxxxxx/ yyyy/ NA/ 3/ Zzzzz	Completed	ddmmmyyyy (xx)	Visit Window	Xxxxxxxxxxxxx	Minor

\$: Stage 2 = Moderate, Stage 3 = Severe

Note: - = unknown or not evaluated, N/A = not applicable, NA = North America, EU = Europe

Note: Study Day 1 is the first day of study treatment.

Analysis dataset: ADxx.SAS7BDAT;
Date/time of run: ddmmmyyyy:hh:mm

oprogram name>

Programming Note:

Sort listing by treatment group (lowest MT8 to highest and then Vehicle) and patient ID. If a patient is not treated or a screen failure display 'Not Treated' or 'Screen Failure' in first column as Treatment group and sort these patients at the end of the listing.

This document is confidential.

SAP Version: 1.0, 31-May-2024

Controlled Document ID: 3903A.02, Effective Date 31-Aug-2020

Sponsor: Recordati Rare Diseases; Protocol No.: REC0559-B-001

Listing 16.2.2.2 Missing Visits and Assessments due to COVID-19 (Enrolled Set)

Patient ID/ Treatment group/ Region/ Disease stage \$/ Study eye	End of Treatment Status	Visit	Missing Assessment	Reason
Xxxxxx/ yyyy/ EU/ 2/ zzzzzz	Completed	Visit x	All	Patient not able to come to site due to COVID-19
		Visit y	Vital Signs	Covid-19 related
Xxxxxx/ yyyy/ EU/ 2/ zzzzzz	Other: xxx	Visit y	Physical Examination	Due to COVID-19
Xxxxxx/ yyyy/ NA/ 3/ Zzzzz	Completed	Visit z	Spirometry	Not performed because of covid-19

\$: Stage 2 = Moderate, Stage 3 = Severe

Note: - = unknown or not evaluated, N/A = not applicable, NA = North America, EU = Europe

Analysis dataset: ADxx.SAS7BDAT;
Date/time of run: ddmmmyyyy:hh:mm

ogram name>

Programming Note:

Sort listing by treatment group (lowest MT8 to highest and then Vehicle) and patient ID. If a patient is not treated or a screen failure display 'Not Treated' or 'Screen Failure' in first column as Treatment group and sort these patients at the end of the listing. All missing assessments of a visit are listed separately. If a visit is missed completely so that no assessments are available, list the term 'All'.

Sponsor: Recordati Rare Diseases; Protocol No.: REC0559-B-001

Listing 16.2.3.1 Inclusion/Exclusion (Enrolled Set)

Patient ID/ Treatment group/ Region/ Disease stage \$/ Study eye	Failed Criterion	Description	Protocol Version */ Additional Version Information
Xxxxxx/ yyyy/ EU/ 2/ zzzzzz	INCL03	Xxxxxxxxxxxxxxxxxxxxxxxxxxxxxxxxxxxxxxx	1.0/
Xxxxx	EXCL02	Xxxxxxxxxxxxx	2.0/ xxxx xxxxxxxx

^{*:} Protocol version under which the patient failed the inclusion or met the exclusion criteria

Note: - = unknown or not evaluated, N/A = not applicable, NA = North America, EU = Europe

Analysis dataset: ADxx.SAS7BDAT;
Date/time of run: ddmmmyyyy:hh:mm

program name>

Programming Note:

See section 15 for Format of output in the SAP. Only patients with failed inclusion or exclusion criteria are listed. If a patient is treated display information of treatment group and randomisation strata.

^{\$:} Stage 2 = Moderate, Stage 3 = Severe

Listing 16.2.3.2 Analysis Populations (Enrolled Set)

					Sub-population	ons
Patient ID/ Treatment group/ Region/ Disease stage \$/ Study eye	Safety Set (SAF)/ Reason for Exclusion	Modified Intention to Treat Set (mITT)/ Reason for Exclusion	Per-Protocol Set (PP)/ Reason for Exclusion	xxxxxxx	ууууууу	ZZZZZZZZ
Xxxxx/ yyyy/ EU/ 2/ zzzzzz	Yes	No/ xxxxxxx xxxxx	No/ xxxxxx	ZZZ	WWW	www
Xxxxx/ yyyy/ EU/ 2/ zzzzzz	Yes	Yes	Yes	ZZZ	www	www
Xxxxxx/ yyyy/ NA/ 2/ zzzzzz	Yes	Yes	Yes	ZZZ	www	www
Xxxxx/ yyyy/ EU/ 2/ zzzzzz	Yes	Yes	Yes	222	www	www
Xxxxx/ yyyy/ EU/ 3/ zzzzzz	Yes	Yes	Yes	ZZZ	www	www
Xxxxx/ yyyy/ NA/ 3/ zzzzzz	Yes	Yes	Yes	222	WWW	www

^{\$:} Stage 2 = Moderate, Stage 3 = Severe

Note: - = unknown or not evaluated, N/A = not applicable, NA = North America, EU = Europe

Analysis dataset: ADxx.SAS7BDAT;
Date/time of run: ddmmmyyyy:hh:mm

program name>

Programming Note:

Additional Sub-populations are based on the availability of data and will be defined before DB Lock. They are detailed in the SAP section 5. Include only sub-populations that have data available at the end of the study Sort listing by treatment group (lowest REC 0/0559 to highest and then Vehicle) and patient ID. If a patient is not treated or a screen failure display 'Not Treated' or 'Screen Failure' in first column as Treatment group and sort these patients at the end of the listing.

This document is confidential.

SAP Version: 1.0, 31-May-2024

Controlled Document ID: 3903A.02, Effective Date 31-Aug-2020

Sponsor: Recordati Rare Diseases; Protocol No.: REC0559-B-001

Listing 16.2.4.1 Demographics (Enrolled Set)

Patient ID/ Treatment group/ Region/ Disease stage \$/ Study eye	Previous Patient ID if re- screened	Year of Birth/ Age (years) §	Sex	Childbearing potential?	Race/ Ethnicity #	Iris color	Weight (kg)	Height (cm)	Alcohol status	Smoking status
Xxxxx/ REC 0/0559 0.5 µg/day/ NA/ 2/ Left	N/A	уууу/ хх	Male	N/A	White/ Not Hispanic or Latino	Blue	xx.x	xxx.x	Current	Former
Xxxxx/ REC 0/0559 0.5 µg/day/ EU/ 3/ Left	xxxxx	уууу/ хх	Female	Yes	African American	Light Brown	xx.x	xxx.x	Never	Former
Xxxxx/ yyyy/ zz/ v/ uuuuuu	N/A	уууу/ хх	Male	N/A	Native Hawaiian or other Pacific Islander	Dark Brown	xx.x	xxx.x	-	Current
Xxxxx/ yyyy/ zz/ v/ uuuuuu	N/A	уууу/ хх	Male	N/A	Other: xxxx	Blue	XX.X	xxx.x	Former	Never
Xxxxx/ yyyy/ zz/ v/ uuuuuu	N/A	уууу/ хх	Female	No	American Indian or Alaska Native	Blue	xx.x	xxx.x	Never	-

^{\$: 2 =} Moderate, 3 = Severe

Note: - = unknown or not evaluated, N/A = not applicable, NA = North America, EU = Europe

Analysis dataset: ADxx.SAS7BDAT;

Programming Note:

See section 15 for Format of output in the SAP. Sort listing by treatment group (lowest MT8 to highest and then Vehicle) and patient ID. If a patient is not treated or a screen failure display 'Not Treated' or 'Screen Failure' in first column as Treatment group and sort these patients at the end of the listing.

This document is confidential.

SAP Version: 1.0, 31-May-2024

Controlled Document ID: 3903A.02, Effective Date 31-Aug-2020

S: At screening: derived using 01-Jan-

sirth year> and date of informed consent

^{#:} Available for patients from NA only

Sponsor: Recordati Rare Diseases; Protocol No.: REC0559-B-001

Listing 16.2.4.2 Medical History Other Than NK in Study Eye (Enrolled Set)

Patient ID/ Treatment group/ Region/ Disease stage \$/ Study eye	Medical History Number	System Organ Class/ Preferred Term Verbatim	Start Date/ Stop Date/ Duration	Ocular condition/ Eye
Xxxxx/ REC 0/0559 0.5 μg/day/ NA/ 2/ Right	1	Xxxxxx/ Yyyyy/ XXXXX	ddMMMyyyy/ ddMMMyyyy/ 3 days	Yes/ Right *
	2	Xxxxxx/ Yyyyy/ xxxxxxx	ddMMMyyyy/ ddMMMyyyy/ 5 days	No
Xxxxx/ yyyy/ zz/ v/ uuuuuu	1	Xxxxxxxx/ Yyyy/ Xxxxxxxxxx xxxx	ddMMMyyyy/ Ongoing	No

^{\$:} Stage 2 = Moderate, Stage 3 = Severe

Note: - = unknown or not evaluated, N/A = not applicable, NA = North America, EU = Europe

Note: MedDRA version <version> is used. Analysis dataset: ADxx.SAS7BDAT;

Date/time of run: ddmmmyyyy:hh:mm

program name>

Programming Note:

Sort listing by treatment group (lowest REC 0/0559 to highest and then Vehicle) and patient ID, start date, SOC and PT. If a patient is not treated or a screen failure display 'Not Treated' or 'Screen Failure' in first column as Treatment group and sort these patients at the end of the listing. In case an end date is missing and/or the event is ongoing the term 'Ongoing' will be presented. In case of ocular condition present in the study eye it will be flagged with '*'. Insert MedDRA version in footnote <version> place holder.

^{*:} Study eye

Sponsor: Recordati Rare Diseases; Protocol No.: REC0559-B-001

Listing 16.2.4.3 Neurotrophic Keratitis (NK) Medical History in Study Eye (Enrolled Set)

Patient ID/ Treatment group/ Region/ Disease stage \$/ Study eye	Date of first Diagnosis/ Time since first Diagnosis (weeks)	Disease stage at Screening	Current Episode the first?/ Number of Episodes	Main underlying Cause of NK	Other underlying Causes	History of NK surgical or procedural Treatment?/ History of NK Drug Treatment?/ Any other Treatment
Xxxxx/ REC 0/0559 0.5 µg/day/ NA/ 2/ Right	Ddmmmyyyy/ xx	2 (Moderate)	Yes	Herpes simplex	Other: xxxxx, Ocular surgery: xxxx	Yes/ Yes/ Xxxxxxxx
Xxxxx/ yyyy/ zz/ v/ uuuuuu	Ddmmmyyyy/ xx	3 (Severe)	No/ 3	Herpes zoster	Neurosurgical procedure: xxxxx, Ocular surgery: xxxx	Yes/ No/ -
Xxxxx/ yyyy/ zz/ v/ uuuuuu	Ddmmmyyyy/ xx	2 (Moderate)	Yes	Neurosurgical procedure: xxxxx	Herpes zoster	Yes/ No/ -
Xxxxx/ yyyy/ zz/ v/ uuuuuu	Ddmmmyyyy/ xx	2 (Moderate)	Yes	Ocular surgery: xxxxx	Herpes zoster	Yes/ No/ -
Xxxxx/ yyyy/ zz/ v/ uuuuuu	Ddmmmyyyy/ xx	3 (Severe)	Yes	Herpes simplex	No	No/ No/ xxxxxxx
Xxxxx/ yyyy/ zz/ v/ uuuuuu	Ddmmmyyyy/ xx	2 (Moderate)	No/ -	Other: xxxx	Other: xxxxxx	No/ Yes/ xxxxx

^{\$:} Stage 2 = Moderate, Stage 3 = Severe

Note: - = unknown or not evaluated, N/A = not applicable, NA = North America, EU = Europe

Note: Time since first diagnosis (weeks) is calculated as ((date of informed consent signature) - (date of first diagnosis)) / 7. If only month and year are available, the day = 15 will be assumed. If only year is available, month = 6 and day = 15 will be assumed. In case the imputed date is greater than the date of signed informed consent (IC), then the date of IC will be used as date of first NK diagnosis.

Analysis dataset: ADxx.SAS7BDAT; Date/time of run: ddmmmyyyy:hh:mm

program name>

Programming Note:

See section 15 for Format of output in the SAP. Sort listing by treatment group (lowest MT8 to highest and then Vehicle) and patient ID. If a patient is not treated or a screen failure display 'Not Treated' or 'Screen Failure' in first column as Treatment group and sort these patients at the end of the listing. In case multiple underlying causes are available then they are all listed and separated by commas. If no other underlying causes (that are not the main cause) are available as captured in the CRF then display 'No'.

This document is confidential.

SAP Version: 1.0, 31-May-2024

Controlled Document ID: 3903A.02, Effective Date 31-Aug-2020

Sponsor: Recordati Rare Diseases; Protocol No.: REC0559-B-001

Listing 16.2.4.4 Prior and Concomitant Medication (Enrolled Set)

Patient ID/ Treatment group/ Region/ Disease stage \$/ Study eye	ATC Level 2/ ATC Level 3/ Preferred Term Medication	Start Date/ Stop Date/ Duration	Prior or Concomitant	Dose (unit)/ Dose Form/ Frequency/ Route	Ophthalmic?/ Eye	Reason
Xxxxx/ REC 0/0559 0.5 μg/day/ NA/ 2/ Right	Xxxxxx/ Yyyyy/ Xxxx/ wwwwwwwwwww	ddMMMyyyy/ ddMMMyyyy/ 3 days	Prior	100 (mg)/ Tablet/ QH/ Oral	No	Medical History: xx, yy
Xxxxx/ yyyy/ zz/ v/ uuuuuu	Xxxxxxxx/ Yyyy/ Xxxxxx/ wwwwwww	ddMMMyyyy/ Ongoing	Concomitant	5 mL/ Suspension/ BID/ Intraocular	Yes/ Right *	Rescue Treatment for NK: Other: xxxx

^{\$:} Stage 2 = Moderate, Stage 3 = Severe

Note: - = unknown or not evaluated, N/A = not applicable, NA = North America, EU = Europe

*: Study eye

Note: WhoDD version <version> is used. Analysis dataset: ADxx.SAS7BDAT;

Date/time of run: ddmmmyyyy:hh:mm

program name>

Programming Note:

Sort listing by treatment group (lowest REC 0/0559 to highest and then Vehicle) and patient ID, ATC level and PT. If a patient is not treated or a screen failure display 'Not Treated' or 'Screen Failure' in first column as Treatment group and sort these patients at the end of the listing. In case an end date is missing and/or the medication is ongoing the term 'Ongoing' will be presented. Reasons will be concatenated by '/'. In case of multiple events per reason e.g. Adverse Events present as 'Adverse Event: ' and then list and separate the event numbers by ','. In case ophthalmic medication is taken for the study eye it will be flagged with '*'. Insert WhoDD version in place holder <version> in footnote.

This document is confidential.

SAP Version: 1.0. 31-May-2024

Controlled Document ID: 3903A.02, Effective Date 31-Aug-2020

Sponsor: Recordati Rare Diseases; Protocol No.: REC0559-B-001

Listing 16.2.4.5 Prior and Concomitant Ocular Interventions (Enrolled Set)

Patient ID/ Treatment group/ Region/ Disease stage \$/ Study eye	OI Nr.	Type of Ocular Intervention/ System Organ Class/ Preferred Term/ Description	Date of Intervention (Study day)	Prior or Concomitant	Resolved?	Eye	Reason
Xxxxx/ REC 0/0559 0.5 µg/day/ NA/ 2/ Right	1	Vitrectomy/ Xxxxxx/ Yyyyyyyy/ Wwwwwwwwwww/	ddMMMyyyy	Prior	Yes	Both	Medical History: xx, yy
	2	Xxxxxxx/ yyyyy/ Yyyyyyyyy/ Wwwwwwwwww/	ddMMMyyyy	Prior	No	Left *	Medical History: xx
Xxxxx/ yyyy/ zz/ v/ uuuuuu	1	Other Laser/ xxxxx/ Yyyyyyyyy/ Wwwwwwwwwww/	ddMMMyyyy	Concomitant	No	Right	Adverse Event: xx/ Rescue Treatment for NK: Other: xxxx

OI: Ocular Intervention

Note: - = unknown or not evaluated, N/A = not applicable, NA = North America, EU = Europe

Note: MedDRA version <version> is used.

Analysis dataset: ADxx.SAS7BDAT;
Date/time of run: ddmmmyyyy:hh:mm

program name>

Programming Note:

Sort listing by treatment group (lowest REC 0/0559 to highest and then Vehicle) and patient ID, start date and type. If a patient is not treated or a screen failure display 'Not Treated' or 'Screen Failure' in first column as Treatment group and sort these patients at the end of the listing. Reasons will be concatenated by '/'. In case of multiple events per reason e.g. Adverse Events present as 'Adverse Event: ' and then list and separate the event numbers by ','. Insert MedDRA version in footnote <version> place holder.

^{\$:} Stage 2 = Moderate, Stage 3 = Severe

^{*:} Study eye

Sponsor: Recordati Rare Diseases; Protocol No.: REC0559-B-001

Listing 16.2.4.6 Prior and Concomitant Surgery and Procedures (Other than Ocular) (Enrolled Set)

Patient ID/ Treatment group/ Region/ Disease stage \$/ Study eye	Surgery/ Procedure Number	System Organ Class/ Preferred Term/ Surgery/Procedure	Date of Surgery/Procedure	Prior or Concomitant	Reason
Xxxxx/ REC 0/0559 0.5 µg/day/ NA/ 2/ Right	1	Xxxxxxxxxx xxxxx/ Yyyyyyyy/ zzzzzzzzzzzzzzzzzzz	ddMMMyyyy	Prior	Medical History: xx, yy
Xxxxx/ yyyy/ zz/ v/ uuuuuu	1	xxxxxxxx/ Yyyyyyyy/ zzzzzzzzzzzzzzzzzzzz	ddMMMyyyy	Concomitant	Adverse Event: xx

^{\$:} Stage 2 = Moderate, Stage 3 = Severe

Note: - = unknown or not evaluated, N/A = not applicable, NA = North America, EU = Europe

Note: MedDRA version <version> is used.

Analysis dataset: ADxx.SAS7BDAT;

Programming Note:

Sort listing by treatment group (lowest REC 0/0559 to highest and then Vehicle) and patient ID, start date and procedure. If a patient is not treated or a screen failure display 'Not Treated' or 'Screen Failure' in first column as Treatment group and sort these patients at the end of the listing. Reasons will be concatenated by '/'. In case of multiple events per reason e.g. Adverse Events present as 'Adverse Event: ' and then list and separate the event numbers by ','. Insert MedDRA version in footnote <version> place holder.

Sponsor: Recordati Rare Diseases; Protocol No.: REC0559-B-001

Listing 16.2.4.7 Schirmer Test (Enrolled Set)

Patient ID/ Treatment group/ Region/ Disease stage \$/ Study eye	Date of Measurement	Right Eye Result (mm)/Reason Not Done	Left Eye Result (mm)/Reason Not Done
Xxxxx/ REC 0/0559 0.5 μg/day/ NA/ 2/ Right	ddmmmyyyy	Xxx	Xxxx
Xxxxx/ yyyy/ zz/ v/ uuuuuu	ddmmmyyyy	Xxxxxxxxxxxx x xxx xxxxxxx	Xxxxx

\$: Stage 2 = Moderate, Stage 3 = Severe

Note: - = unknown or not evaluated, N/A = not applicable, NA = North America, EU = Europe

Analysis dataset: ADxx.SAS7BDAT;

Programming Note:

See section 15 for Format of output in the SAP. Sort listing by treatment group (lowest REC 0/0559 to highest and then Vehicle) and patient ID, start date and procedure. If a patient is not treated or a screen failure display 'Not Treated' or 'Screen Failure' in first column as Treatment group and sort these patients at the end of the listing.

Sponsor: Recordati Rare Diseases; Protocol No.: REC0559-B-001

Listing 16.2.5.1.1 Study Drug Dosing (Enrolled Set)

Patient ID/ Treatment group/ Region/ Disease stage \$/ Study eye	Date and Time of first Dose/ Date and Time of last Dose/ Duration	Interrupted/ Decided by	Interruption Start Date/ Interruption End Date/ Duration	Numbers of doses missed
Xxxxx/ REC 0/0559 0.5 µg/day/ NA/ 2/ Right	Ddmmmyyyy hh:mm/ DDmmmyyyy hh:mm/ X days	Yes/ Investigator	Ddmmmyyyy/ DDmmmyyyy/ X days	Xxx
Xxxxx/ yyyy/ zz/ v/ uuuuuu	Ddmmmyyyy hh:mm/ DDmmmyyyy hh:mm/ X days	No	N/A	N/A
Xxxxx/ yyyy/ zz/ v/ uuuuuu	Ddmmmyyyy hh:mm/ DDmmmyyyy hh:mm/ X days	No	N/A	N/A
Xxxxx/ yyyy/ zz/ v/ uuuuuu	Ddmmmyyyy hh:mm/ DDmmmyyyy hh:mm/ X days	No	N/A	N/A

\$: Stage 2 = Moderate, Stage 3 = Severe

Note: - = unknown or not evaluated, N/A = not applicable, NA = North America, EU = Europe

Note: Duration of exposure (days) = (date of last treatment administration - date of first treatment administration) + 1.

Note: Duration of Interruption (days) = (interruption end date - interruption start date) + 1.

Analysis dataset: ADxx.SAS7BDAT;

Programming Note:

See section 15 for Format of output in the SAP. Sort listing by treatment group (lowest REC 0/0559 to highest and then Vehicle) and patient ID and visit.

Sponsor: Recordati Rare Diseases; Protocol No.: REC0559-B-001

Listing 16.2.5.1.2 Study Drug Dispensation and Compliance (Enrolled Set)

Patient ID/ Treatment group/ Region/ Disease stage \$/ Study eye	Visit	Date of Dispensation	Kit Numbers/ Reason Not Done	Date of Previous Visit	Numbers of used BFS	Comment	Expected number of used BFS/ Overall Compliance (%)
Xxxxx/ REC 0/0559 0.5 µg/day/ NA/ 2/ Right	Visit x	Ddmmmyyyy	Ххх, ууу	N/A	Xxx	Xxxxxx	
-	Visit y	Ddmmmyyyy	Xxxxxxxxxxxx	Ddmmmyyyy	Xxx	_	
		Ddmmmyyyy	Xxx	Ddmmmyyyy	Xxx	-	XX.X
Xxxxx/ yyyy/ zz/ v/ uuuuuu	Visit x	Ddmmmyyyy	Xxx	N/A	Xxx	-	
	Visit y	Ddmmmyyyy	Xxx	Ddmmmyyyy	Xxx	-	
		Ddmmmyyyy	Xxx	Ddmmmyyyy	Xxx	-	XX.X

BFS: Blow Fill Seals

\$: Stage 2 = Moderate, Stage 3 = Severe

Note: - = unknown or not evaluated, N/A = not applicable, NA = North America, EU = Europe

Note: Overall compliance (%) is calculated as (Number of used BFS containers) / [4 * (number of BFS to be used based on actual number of days of treatment)] * 100. Non-compliance is defined as <math>< 80% or > 120% overall compliance.

Analysis dataset: ADxx.SAS7BDAT;

Date/time of run: ddmmmyyyy:hh:mm

program name>

Programming Note:

See section 15 for Format of output in the SAP. Sort listing by treatment group (lowest REC 0/0559 to highest and then Vehicle) and patient ID and visit.

Sponsor: Recordati Rare Diseases; Protocol No.: REC0559-B-001

Listing 16.2.5.1.3 Patient Supply Accountability (Enrolled Set)

Patient ID/ Treatment group/ Region/ Disease stage \$/ Study eye	Visit	Kit ID/ Lot ID/ Date of Expiry	Kit Type (unit)	Quantity Dispensed (Kits)/ IP Units Dispensed (BFS)	Item Status/ Date Returned	Condition/ Quantity of returned Kit	IP Units unused (BFS)	Comment
Xxxxx/ REC 0/0559 0.5 µg/day/ NA/ 2/ Right	Visit x	Xxxx/ yyyyy/ ddmmmyyyy	Хххх (уууу)	Хх/ ууу	Returned/ ddmmmyyyy	Good/ xxx	Xxx	-
		Xxxx/ yyyyy/ ddmmmyyyy	Хххх (уууу)	Хх/ ууу	Returned/ ddmmmyyyy	Good/ xxx	Xxx	-
		Xxxx/ yyyyy/ ddmmmyyyy	Хххх (уууу)	Хх/ ууу	Returned/ ddmmmyyyy	Damaged/ xxx	Xxx	-
		Xxxx/ yyyyy/ ddmmmyyyy	Хххх (уууу)	Хх/ ууу	Returned/ ddmmmyyyy	Unopened/ xxx	Xxx	-
			Хххх (уууу)	Xx/ yyy	Returned/ ddmmmyyyy	Good/ xxx	Xxx	-
